2.1.2.3 Multiple assessments within visit windows

It is possible that multiple assessments of a subject fall into the same visit-window (e.g. due to unscheduled visits). All results (scheduled and unscheduled) will be displayed in listings, but only one value (observed or derived) will be selected for summary statistics by visit-window. If multiple unscheduled visits within visit window are allocated to the same missed scheduled visit:

For **quantitative variables**, the unscheduled assessment closest to the target day will be selected. If more than one assessment is at the same distance to the target day, the later one will be selected. For tables displaying the worst case scenario, such as notable abnormalities, all assessments within a visit window will be used to identify the worst (e.g. the maximum or the minimum depending on parameter). Where applicable it will be defined for each parameter what the worst case is.

For **qualitative variables**, the worst record is selected; it is noted that in the relevant data subsection, worst case is always well defined.

Note that “Last assessment on study drug” is not like other visit-windows where multiple assessments could occur. The assessment to be summarized at that time point is the last on drug observation which is the last observation a subject has while he or she is on fingolimod. Therefore, the above multiple assessment rules do not apply.

In addition, the multiple assessment rules do not apply to the first dose/second dose / restart dose (if applicable) monitoring data.

2.2 Analysis sets

Full Analysis Set (FAS): The FAS comprises all subjects who have signed the Informed Consent and who have received at least one dose of study treatment. The FAS will be used for the summary of demography and baseline characteristics as well as for all efficacy analyses.

Safety Set (SAF): The SAF includes all subjects who have signed the Informed Consent and who have received at least one dose of study treatment. The Safety Set is identical to FAS in this study and will be used for all safety analyses in the final analysis.

All screened subjects (SCR): The SCR set comprises all subjects who have signed the Informed Consent and were screened.

2.2.1 Subgroup of interest

Subgroups for efficacy safety analyses:

- Age at baseline (Adult, Child): adult group is defined as subjects who have baseline age ≥ 18 ; child group is defined as subjects who have baseline age < 18 . This subgroup is defined to assess the efficacy and safety of fingolimod on adult and pediatric subjects separately.

2.3 Patient disposition, demographics and other baseline characteristics

2.3.1 Patient disposition

The number and percentage of subjects who were screened but did not continue into the Treatment Period will be presented, along with the reason for discontinuation being “Screen Failure”. Data collected on the Disposition CRF page will be used to summarize this information. The summary will be on the SCR set.

The number and percentage of subjects who completed the treatment period on treatment or prematurely discontinued the study treatment will be presented, along with the primary reason for discontinuation. Data collected on the Treatment disposition CRF page will be used to summarize this information. The summary will be on the FAS.

The number and percentage of subjects who completed the study (i.e. the Treatment Period) or prematurely discontinued the study prior to the end of the treatment period will be presented, along with the primary reason for discontinuation. Data collected on the Study disposition CRF page will be used to summarize this information. The summary will be on the FAS. Subjects who prematurely discontinue the study treatment will be listed along with the reason for discontinuation.

Protocol deviations will be summarized by deviation categories for the FAS. In addition, protocol deviations that led to exclusion from the analysis set will be listed.

All summaries in this section will be presented by age group and then overall.

2.3.2 Background and demographic characteristics

All analyses in this section will be presented by age group on FAS.

Background characteristics include subject demographic characteristics (sex, race and ethnicity collected on the Demography CRF), age at screening, height, body weight and BMI at baseline.

Age, baseline height, body weight and derived BMI will be presented. These variables will be summarized for the FAS using frequency distributions (for categorical variables) and descriptive statistics of mean, standard deviation, minimum, median and maximum (for continuous variables).

2.3.3 MS baseline disease characteristics

All analyses in this section will be presented by age group on FAS.

MS baseline characteristics, MS disease history and MS medication history will be summarized by age group and then overall for the FAS.

MS baseline characteristics include baseline EDSS and key MRI parameters (e.g. number of Gd-enhancing T1 lesions and T2 lesion volume).

MS disease history includes duration of MS since diagnosis (years), duration of MS since first symptom (years), number of relapses in the last 12 months prior to screening, number of relapses in the 12 to 24 months prior to screening, and time since onset of most recent relapse (months) prior to screening.

Duration of MS since diagnosis (years) will be derived as $[(\text{first dose date} - \text{MS diagnosis start date} + 1) / 365.25]$. Duration of MS since first symptom (years) will be derived as $[(\text{first dose date} - \text{first MS symptom date} + 1) / 365.25]$. Time since onset of most recent relapse (months) will be derived as $[(\text{first dose date} - \text{most recent relapse onset date} + 1) / (365.25 / 12)]$. In these calculations, partial dates (if any) will be imputed according to the rules specified in [Section 5.1.4.1](#).

MS medication history of previous disease-modifying drugs (coded by World Health Organization (WHO) drug dictionary) will be summarized. The number and proportion of treatment-naïve subjects (i.e. subjects who have not been treated with any disease-modifying drug before study enrollment) will also be presented. Approved MS disease-modifying drugs list: interferon beta-1a, interferon beta-1b, peginterferon beta-1a, glatiramer acetate, natalizumab, mitoxantrone hydrochloride, mitoxantrone, dimethyl fumarate, fumaric acid, teriflunomide, fingolimod, daclizumab, siponimod, ozanimod, diroximel fumarate, monomethyl fumarate, cladribine, alemtuzumab, ocrelizumab, ofatumumab, ponesimod, etc.

2.3.4 Medical history

Medical history will be summarized by age group on the FAS (or listed for the Child group if more appropriate). Any condition entered on the Medical History CRF will be coded using the Medical Dictionary for Drug Regulatory Affairs (MedDRA) dictionary. The medical history will be summarized by primary system organ class (SOC) and preferred term.

2.4 Treatments (study treatment, concomitant therapies, compliance)

2.4.1 Exposure to study treatment / compliance

The Safety Set will be used for the analyses in this section. Summaries will be presented by age group and then overall.

Duration of exposure to study drug expressed in days is defined as the number of days spent on study treatment. Intermediate treatment interruptions will be subtracted from drug exposure, i.e. the duration of exposure to study treatment (in days) will be calculated as (last dose date – first dose date + 1 – Σ [days with temporary study treatment interruption]), where any day with no drug taken is considered a study treatment interruption.

Exposure to investigational study drug will be summarized with number and percentage of subjects by time category, and with summary statistics of the number of patient years of exposure.

Duration of exposure to study treatment will be summarized descriptively by duration category (i.e. \geq 1 month, \geq 2 months, \geq 3 months, \geq 6 months, \geq 9 months, \geq 12 months, \geq 15 months, \geq 18 months, \geq 21 months). Descriptive statistics of duration in days will also be provided. The number of patient years is calculated as the sum of the duration of exposure for all subjects in the group.

Compliance to the study treatment administration schedule will be calculated as duration of exposure to study treatment in (days) / duration of on-treatment period (as defined in [Table 2-1](#)) (in days) \times 100%. This rule means that compliance will be measured during the time interval the subject took study treatment, i.e. premature discontinuation from study treatment will not be considered non-compliance. Compliance to study treatment administration will be summarized descriptively on the SAF. In addition, compliance will be summarized with cumulative number and percentage of subjects in each compliance category (i.e. \geq 20%, \geq 30%, \geq 40%, \geq 50%, \geq 60%, \geq 70%, \geq 80%, \geq 90%, \geq 95%, \geq 98%, = 100%).

2.4.2 Prior, concomitant and post therapies

Analyses described in this section will be performed on the SAF. Summaries will be presented by age group (or listings for the Child group if more appropriate) and then overall.

2.4.2.1 Concomitant medication

Records on the Concomitant Medications CRF page will be coded using the WHO drug dictionary. All medications will be classified as prior, concomitant or post study treatment discontinuation medication as follows:

- Prior medications are defined as drugs taken and stopped prior to first dose of study medication.
- Concomitant medications are defined as drugs taken at least once between the first and last dose of study medication (including those which were started prior to first dose and continued into the treatment period).

- Post-study treatment discontinuation medications are defined as drugs started after the discontinuation of study medication.

Medications will be categorized into one (and only one) of the above classes based on recorded or imputed start and end dates. When incomplete or missing, dates will be imputed according to Novartis standards (details will be given in programming datasets specifications (PDS) document). If both the start date and the end date are completely missing and medication has not been collected on the “Previous MS Disease Modifying Treatment” page, the medication will be classified into concomitant medication category.

Medications in each of these three categories will be summarized by Anatomical Therapeutic Chemical (ATC) code and preferred term (and/or listed, if appropriate). ATC level 1 and level 3 (e.g. M [Musculo-skeletal system], M01A [anti-inflammatory and anti-rheumatic products, non-steroids], etc.) will be used.

Data collected from the Previous MS disease modifying treatment pages will not be included in this summary.

2.4.2.2 Surgical and medical procedures

Records on the Prior or Concomitant non-drug therapies/procedures CRF page will be coded using the MedDRA dictionary. All procedures will be classified as prior, concomitant or post-study treatment discontinuation procedure, in the same way as done for concomitant medications. Surgical and medical procedures in each of these three categories will be summarized separately by system organ class and preferred term (and/or listed, if appropriate).

Imputation rules for start and end dates will be the same as for the concomitant medications.

2.5 Analysis of the primary objective

All analyses for primary objective will be conducted using the FAS.

2.5.1 Primary endpoint

Two variables are required for the calculation of the ARR (excluding covariates):

- The cumulative number of confirmed MS relapses by subject is the response variable in the negative binomial model. All confirmed relapses with a start date on or after the date of first administration of study drug and prior to or on the end of treatment period date will be included in the analysis. Additional details are provided in [Section 5.1.4](#).
- The definition of a confirmed MS relapse is one accompanied by a clinically relevant change in the EDSS assessment, i.e. an increase of at least 0.5 points on the EDSS (total) score, or an increase of at least 1 point on at least two Functional scores (FSs), or an increase of at least 2 points on at least one FS, excluding changes involving bowel/bladder or cerebral FS, compared to the last EDSS assessment taken in the absence of (confirmed or unconfirmed) relapse and prior to the current relapse. EDSS obtained on the date as indicated on the Summary of MS Relapse eCRF page will be used. If such EDSS assessment is missing or not meeting the criteria to confirm the relapse, all other EDSS assessments taken within 30 days from the relapse start date (i.e. EDSS assessment date – relapse start date <=30) and before the relapse end date

(EDSS assessment date < relapse end date) will be checked. If at least one of such available EDSS assessments meets the criteria, the relapse is a confirmed relapse. Otherwise, the relapse is considered an unconfirmed relapse.

- The time in study by subject will be used as an offset variable to adjust for the various length subjects have been observed (due to premature study discontinuation) and at-risk of a confirmed MS relapse in the study. Time in study for ARR will be calculated as (end of treatment period date – first dose date+1)/365.25.

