12.4.3 Handling of missing values/censoring/discontinuations

For participants who early withdraw from the study, the number of relapses up to the study discontinuation will be used for the primary analysis. No imputation will be applied to the incomplete study duration.

The primary negative binomial regression model with an offset for the time in study adjusts for missing information (drop-out) under the assumption of non-informative drop-out, information is missing at random, and constant relapse rate over time.

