End of Study (EOS)	EOS, used in the context of individual subjects, refers to EOS visit.
End of Treatment (EOT)	EOT refers to EOT visit. Only subjects who prematurely discontinue study drug but agree to continue to follow the schedule of assessments in the treatment period will have EOT visit.
End of treatment period date	This date is the date of discontinuation/study phase completion as recorded in the Treatment disposition CRF page.
Last assessment on drug	It is the last assessment with non-missing value taken before or on the date of last administration of study drug. No visit windows will be needed for the identification of the last assessment on drug evaluation.

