2.5.3 Handling of missing values/censoring/discontinuations

According to the protocol, subjects who discontinue study treatment should remain in the study and follow the assessment schedule. The primary analysis will use all available data up to the end of treatment period date, irrespective of on or off study treatment.

For subjects who early withdraw from the study, the number of relapses up to the study discontinuation will be used for the primary analysis. No imputation will be applied to the incomplete study duration.

The primary negative binomial regression model with an offset for the time in study adjusts for missing information (drop-out) under the assumption of non-informative drop-out, information is missing at random, and constant relapse rate over time.

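### The CRF page named for the primary ARR end date may cut participants at drug stop, at odds with the SAP's own rule to count data on or off treatment

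*SAP*

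**What the plan says.** - **Count.** SAP 2.5.1 includes confirmed relapses from first dose onward; those starting "prior to or on the end of treatment period date will be included in the analysis".
- **Offset.** The same section computes time in study from first dose to the same end date. It says the offset adjusts for the "various length subjects have been observed (due to premature study discontinuation" (the reason given is leaving the study, not stopping drug).
- **Definition of the end date.** SAP Table 2-1: "This date is the date of discontinuation/study phase completion as recorded in the Treatment disposition CRF page".
- **What that page is used for.** SAP 2.3.1 takes from the Treatment disposition page the numbers who "completed the treatment period on treatment or prematurely discontinued the study treatment".
- **The other page.** SAP 2.3.1 also tabulates those who "completed the study (i.e. the Treatment Period) or prematurely discontinued the study prior to the end of the treatment period", and for these: "Data collected on the Study disposition CRF page will be used to summarize this information".
- **The rule for the primary analysis.** SAP 2.5.3: "The primary analysis will use all available data up to the end of treatment period date, irrespective of on or off study treatment". It rests on the premise that participants who stop drug stay in the study and keep to the assessment schedule.
- **Early withdrawal from the study.** Protocol 12.4.3 says that "the number of relapses up to the study discontinuation will be used for the primary analysis"; SAP 2.5.3 repeats this.

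**The concern.** The SAP describes one analysis and names a data source that appears to deliver another. If the Treatment disposition page holds the drug discontinuation date, as its use in SAP 2.3.1 suggests, a participant who stops drug at Month 12 and is followed to Month 24 contributes only the first 12 months. The on-or-off clause in SAP 2.5.3 would then have almost no effect for the very participants it is written for.

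ARR is the only primary endpoint, and the study has one arm and no hypothesis test, so the meaning of the estimate is the main result. Two programmers, one following Table 2-1 and the other SAP 2.5.3, could produce different primary ARRs. The first would give an on-treatment rate reported as if it held regardless of treatment status. That rate would be too low if relapses are more frequent after drug stop and stoppers remain under observation.

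**Working it through.** **Step 1. Which date the SAP points to.**

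| Text | Points to |
|---|---|
| Table 2-1 names the Treatment disposition page; SAP 2.3.1 uses that page for stopping study treatment | drug stop |
| SAP 2.5.3, on-or-off rule | end of the treatment phase, regardless of drug |
| SAP 2.5.1, reason for the offset | leaving the study |
| Table 2-1, a separate on-treatment period ending at last dose, which the ARR does not use | end of the treatment phase |
| SAP 2.1.2.2, which expects treatment-period data after drug discontinuation | end of the treatment phase |
| SAP 2.1, efficacy data until EOT, glossed as leaving out safety follow-up | mixed: the gloss suggests the end of the phase, but Table 2-1 defines EOT as a visit that only early drug stoppers have |
| SAP 2.5.4, days in study | no end date given |

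The intent is fairly clear, and the named page is the item that does not fit it. No text gives a drug stopper a later date on that page.

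**Step 2. The plan's own precision figure.** Inputs from protocol 12.8.1 and SAP 3.1: ARR 0.25, dispersion k = 1, n = 80. The half-width is 1.96 × sqrt((0.25 + 1 × 0.25²)/80) = 1.96 × 0.0625 = 0.1225. The interval is 0.1275 to 0.3725, which rounds to the stated 0.13 to 0.37. This takes one year per participant. With two years the standard error is 0.0484 and the half-width about 0.095.

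**Step 3. Illustration of the difference.** From the plan: on-drug ARR 0.25; 0.20, the planned drop-out rate, borrowed as the share who stop drug; and 0.40 and 0.63, placebo ARRs in protocol Table 12-1 (0.63 is the Chinese one), borrowed as off-drug rates. Assumed: the stop time t in years, the share s of stoppers who stay to two years, and an off-drug ARR r between 0.25 and 0.63.

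Per participant, on-drug time = 0.8 × 2 + 0.2 × t, and off-drug time = 0.2 × s × (2 − t).

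On-or-off ARR = (on-drug time × 0.25 + off-drug time × r) / (on-drug time + off-drug time). The ARR cut at drug stop is 0.250 throughout.

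Example with t = 1, s = 1, r = 0.63: (1.8 × 0.25 + 0.2 × 0.63)/2 = 0.576/2 = 0.288. The cut estimate is 1 − 0.250/0.288 = 13% lower.

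| Drug stop | Share staying | r = 0.25 | r = 0.40 | r = 0.63 |
|---|---|---|---|---|
| 6 months | all | 0.250 | 0.273 | 0.307 |
| 12 months | all | 0.250 | 0.265 | 0.288 |
| 18 months | all | 0.250 | 0.258 | 0.269 |
| 6 months | half | 0.250 | 0.262 | 0.281 |
| 12 months | half | 0.250 | 0.258 | 0.270 |
| 18 months | half | 0.250 | 0.254 | 0.260 |
| any | none | 0.250 | 0.250 | 0.250 |

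The largest gap in the table is 0.307 − 0.250 = 0.057, or 19% lower. If 30% stopped at 6 months and all stayed, r = 0.63 would give (1.55 × 0.25 + 0.45 × 0.63)/2 = 0.3355, a gap of 0.0855. That is still below either half-width in Step 2. These are crude rates, not output from the covariate-adjusted model.

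**The case against.** The strongest reply is that the SAP's intent is plain. SAP 2.5.3 applies this very date on or off drug, and where the SAP means drug stop it uses other terms, such as last dose date. Table 2-1 also mentions completion of the study phase, which is phase language, and SAP 2.3.1 says which page feeds a table, not which date fields the page holds. This much stands: a reader might infer that participants will be cut at drug stop, and the documents do not establish that, because the CRF is not among them.

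A reader might also infer that the date contradicts protocol 12.4.3. That rule concerns participants who withdraw early from the study. It differs from a drug-stop cut only for someone who stops drug, stays, and leaves later, so it is weak evidence for the point.

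Nor is the rate miscalculated: count and offset end on the same date. The 20% is a drop-out rate; if it means leaving the study at drug stop, the difference is zero. The value 0.63 is a placebo rate, while protocol 6.2.2 lets other MS therapies be considered after permanent drug discontinuation, so it serves as an upper value.

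Finally, adding off-drug time could itself bias the ARR downward if relapses are not sought then. Protocol 9.1.1 asks stoppers to return for EOT and follow-up visits, and its minimum data for abbreviated contacts are treatments and adverse events, with no mention of relapse or EDSS. This objection is sound and shapes the fix.

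None of this removes the conflict: no SAP text excludes the drug-stop reading, and the page named in the definition favours it.

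**Conclusion.** The conflict holds and should be resolved before database lock. As written, the definition can turn the sole primary endpoint into an on-drug rate while SAP 2.5.3 describes it as regardless of drug status. The drug-stop cut is a likely reading and not a certainty. The question is which rate is estimated, not whether the arithmetic is right.

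The size is modest. In the 20% illustration the shift is 0 to 0.057, under half the planned half-width of 0.12. It needs stoppers who stay in the study and relapse more often off drug, and neither can be learned from the documents. Participants who complete on drug are unaffected. Confidence is medium, because the content of the CRF page is inferred from how SAP 2.3.1 uses it.

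**What to change.** 1. In Table 2-1 and SAP 2.5.1, define one end date for both count and offset, regardless of drug status: the earliest of study discontinuation (Study disposition page), the actual Month 24 visit (or Day 720 if that visit is missing), and the last contact at which relapse was assessed. The last element keeps person-time without relapse ascertainment out of the denominator.
2. Use the same date in SAP 2.1 in place of the EOT cut-off, and for days in study in SAP 2.5.4.
3. Reconcile the SAP 2.5.3 premise that stoppers follow the assessment schedule with protocol 9.1.1.
4. Optionally, report the ARR to last dose as a supportive estimate labelled as while on treatment.

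The cost is a wording change and one date derivation, with no new data or visits. The downside is that the reported ARR may be slightly less favourable.

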8.3 Efficacy

MS relapse activity and neurological impairment of MS as measured by Expanded Disability Status Scale (EDSS) (refer to [Section 16.4](#) for EDSS assessment criteria) will be obtained in order to characterize the disease activity.

8.3.1 Efficacy assessment 1

MS relapse

General definition of relapse: Appearance of a new neurological abnormality or worsening of previously stable or improving pre-existing neurological abnormality, separated by at least 30

days from onset of a preceding clinical demyelinating event. The abnormality must be present for at least 24 hours and occur in the absence of fever (< 37.5 °C) or infection.

Definition of confirmed relapse: A relapse must be confirmed by the Treating Physician. It is recommended that this occur within 7 days of the onset of symptoms. A relapse is confirmed when it is accompanied by an increase of at least half a step (0.5) on the EDSS or an increase of 1 point on two different Functional Systems (FS) of the EDSS or 2 points on one of the FS (excluding Bowel/Bladder or Cerebral FS).

Only confirmed relapses will be included in the primary efficacy analysis. However, the relapse-related analyses will be repeated using all relapses to assess the sensitivity of the results.

Reporting of relapse : A participant may report symptoms indicative of a relapse at a scheduled visit or at any other time. Participants will be instructed to immediately contact the treating physician if he/she develops new or re-occurring or worsening neurological symptoms. At each scheduled visit, the participant will also be asked whether any such symptoms have occurred.

Upon reporting of symptoms indicative of a relapse, the treating physician will assess in an appropriate manner whether the symptoms occur in the presence of fever or infection. If fever or infection can be excluded, a neurological examination by the treating physician must be arranged as soon as possible. If fever or infection cannot be excluded, the neurological examination will be postponed until the fever or the infection has ceased (provided, that the symptoms indicative of a relapse are still present). Treatment with steroids should not begin prior to the assessment by the investigator.

Based on results of the neurological examination (change in FS and EDSS scores), the treating physician will assess if the relapse meets the criteria for “confirmed relapse” as per protocol and record relapse on the Summary of MS Relapses eCRF.

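### SAP 2.5.1 sets only upper limits on the EDSS dates that can confirm a relapse, so a reading taken before onset meets the stated formula

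*SAP*

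**What the plan says.** SAP 2.5.1 states the role of the count: "The cumulative number of confirmed MS relapses by subject is the response variable in the negative binomial model". One route to confirmation is "an increase of at least 0.5 points on the EDSS (total) score"; the others are changes in functional system scores. The reference for the increase is a reading "compared to the last EDSS assessment taken in the absence of (confirmed or unconfirmed) relapse and prior to the current relapse".

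The EDSS on the date given on the relapse eCRF page is used first. The fallback then reads "If such EDSS assessment is missing or not meeting the criteria to confirm the relapse, all other EDSS assessments" are considered, limited to those "taken within 30 days from the relapse start date (i.e. EDSS assessment date – relapse start date <=30" and to those meeting a second condition, "EDSS assessment date < relapse end date) will be checked". One hit is enough: "If at least one of such available EDSS assessments meets the criteria, the relapse is a confirmed relapse".

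Protocol 8.3.1 and SAP 2.5.1 both define a confirmed relapse as one that the EDSS change accompanies. On the physician's confirmation, Protocol 8.3.1 adds: "It is recommended that this occur within 7 days of the onset of symptoms". Neither document states an earliest date for the fallback search.

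**The concern.** The formula follows an i.e., so it reads as the definition of the window, and it is the part a programmer will code. It limits how late a confirming EDSS may be, but not how early. Readings taken before onset therefore qualify as candidates.

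The reference reading must be relapse-free, but the candidate readings need not be. A high EDSS recorded during an earlier relapse, from which the participant has since recovered, can exceed the reference by 0.5 or more. It could then confirm a later relapse in which the EDSS did not rise at all. Such an event would enter the response variable of the primary model. An error of this kind can only add to the confirmed count, so it would raise the estimated ARR.

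**Working it through.** **The two conditions.** Let d be the EDSS date minus the relapse start date, and L the relapse end date minus the start date (L is not negative). The formula requires d ≤ 30 and d < L. Any pre-onset reading has d < 0 and meets both.

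**Constructed histories.** I applied the SAP 2.5.1 rule to five histories in which the EDSS on the eCRF-indicated date equals the reference, so there is no true increase. Days count from first dose. A candidate confirms if it is at least 0.5 above the last relapse-free EDSS before onset.

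| Case | EDSS by day | Onset; eCRF-dated EDSS | Reference | Best pre-onset candidate | As written | d from −30 to 30 | d from 0 to 30 |
|---|---|---|---|---|---|---|---|
| A | −10: 2.0 | 200; day 205: 2.0 | 2.0 (day −10) | the reference itself, +0 | no | no | no |
| B | −10: 2.0; 103: 3.5 (in relapse, days 100–130); 180: 2.0 | 300; day 305: 2.0 | 2.0 (day 180) | day 103, d = −197, +1.5 | **confirmed** | no | no |
| C | −10: 3.0; 180: 2.0 | 300; day 305: 2.0 | 2.0 (day 180) | day −10, d = −310, +1.0 | **confirmed** | no | no |
| D | −10: 2.0; 270: 3.5 (in relapse, days 262–285); 290: 2.0 | 298; day 305: 2.0 | 2.0 (day 290) | day 270, d = −28, +1.5 | **confirmed** | **confirmed** | no |
| E | −10: 2.0; 180: 2.5 | 300; day 305: 2.5 | 2.5 (day 180) | day −10, −0.5 | no | no | no |

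As written, three of the five are falsely confirmed. A two-sided 30-day window leaves one, and a lower limit of zero leaves none. In case D the two onsets are 298 − 262 = 36 days apart, so the merging rule in SAP 5.1.4.3 (onsets under 30 days apart) does not absorb the second relapse.

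Case B does not depend on the redacted part of the EDSS schedule. Without the day 180 visit, the screening value of 2.0 becomes the reference, and the day 103 reading is still 3.5 − 2.0 = 1.5 above it. Protocol 8.5.1 requires an EDSS at each unscheduled relapse visit, so a reading like day 103 would normally exist after an earlier relapse.

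**Scale.** The plan's own interval reproduces. With ARR 0.25, k = 1 and n = 80 (SAP 3.1), 0.25 ± 1.96 × √[(0.25 + 0.25²)/80] = 0.25 ± 0.1225, giving 0.1275 to 0.3725 against the stated 0.13 to 0.37. The point does not rest on this figure; it only gives a yardstick.

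Assume 720 days per participant, or 720/365.25 = 1.971 years:

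- 80 participants: 157.7 patient-years; one extra confirmed relapse adds 1/157.7 = 0.0063.
- 100 participants: 197.1 patient-years; one extra adds 1/197.1 = 0.0051.

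At an ARR of 0.25 the expected counts are 39.4 and 49.3 relapses. If between 1 and 10 relapses were falsely confirmed (an assumed range, for illustration), the crude ARR would rise by 0.006 to 0.063 with 80 participants, or by 0.005 to 0.051 with 100. One event is 0.0063/0.1225, about 5%, of the planned half-width at n = 80. Drop-out, or the restriction of the primary model to adults (SAP 2.5.2), would make each event count for somewhat more.

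**The case against.** The intent is not in doubt. The prose before the formula speaks of 30 days from the start date, and a reading from months earlier does not fit that. Both documents say that the change accompanies the relapse. The pre-relapse EDSS is named as the reference, not as a confirming reading. The note to Table 5-1 in SAP 5.1.4.3 also treats the confirming EDSS as one obtained for that purpose. The protocol's 7-day sentence is a recommendation to the physician; it does not contradict the SAP window but points the same way. A programmer who follows the prose may restrict the search to post-onset readings unprompted.

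The route is also narrow. The fallback opens only when the eCRF-dated EDSS is missing or does not confirm. The last relapse-free reading cannot confirm, because it is the reference. Cases B and C disappear if the prose is respected, and case D needs a recent earlier relapse, recovery and a new onset in close succession. There is no hypothesis test (Protocol 12), any error runs against the drug, and SAP 2.5.4 lists relapses with their confirmation status.

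All of this stands, and it limits the likely size. It does not remove the defect: the formula is presented as the definition, and the two-sided reading of the prose still admits case D.

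Two stronger readings are tempting. A reader might infer that the primary ARR is inflated by some stated percentage. That would need the share of unconfirmed relapses, the EDSS visit frequency and the noise in stable readings. The documents give none of these, and the EDSS schedule after screening is partly redacted. A reader might also fault the search because it upgrades relapses and never downgrades them, but that is true of any fallback search, including the corrected one.

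**Conclusion.** Wrong as written. Followed literally, the stated window lets an EDSS from before onset confirm a relapse that had no EDSS increase, contrary to the definition of a confirmed relapse in both documents. The missing lower limit can only add confirmed relapses, so its effect on the primary ARR would be upward.

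The effect is conditional on literal coding, and it is zero if the derivation already uses post-onset readings only. The documents therefore do not show that the primary estimate is biased, only that the rule permits it. The number of affected relapses cannot be derived. Each would add about 0.005 to 0.006 to the crude ARR, assuming 720 days of follow-up for 100 or 80 participants. The supportive analysis of all reported relapses (SAP 2.5.4) does not use the confirmation rule and sets a ceiling on the effect, though it does not repair the primary estimate.

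**What to change.** In SAP 2.5.1, write the window with both limits: 0 ≤ (EDSS assessment date − relapse start date) ≤ 30. Keep the existing condition on the relapse end date, and carry the same inequality into the derived-dataset specification. Only readings on or after onset can then confirm a relapse.

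The cost is one inequality in two documents. No data collection, visit or clinical rule changes. If the derivation has already been programmed, running it with and without the lower limit shows how many relapses, if any, change status.
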